11.3 Reporting of Serious Adverse Events

The Investigator is responsible for ensuring that all SAEs are reported to the Sponsor immediately, but in any event no later than 24 hours of any site staff becoming aware of the event. Initial reports should be followed as soon as possible by detailed written reports. The initial and follow-up reports should identify patients by unique code numbers assigned in the study. The patient's names, personal identification numbers, and/or addresses must not be included. The following information is **mandatory** for the initial report:

- Patient study ID
- Study treatment (blinded, if applicable)
- Start date (time, if relevant) of the study treatment
- Brief description of the event (diagnosis)
- Start date (time, if relevant) of the event
- Seriousness criteria
- Causality assessment

For reported deaths, the Investigator should supply the Sponsor and the IRB/IEC (if applicable) with any additional requested information (e.g. autopsy reports and terminal medical reports).

Detailed instructions describing the procedure of reporting SAEs including Suspected Unexpected Serious Adverse Reactions (SUSARs), *Section 11.4*, will be distributed to the site and all involved parties at the Sponsor and [REDACTED] prior to study start.

As a principle, all SAEs must be documented and medically assessed by the Investigator and the outcome described in the AE section of the eCRF.

Follow-up of Post-Study Survival Information

Sites having patients who are still alive after the entire study has ended will be asked to seek survival information in medical records or databases (including public records).

The patient's survival information after the patient's End-of-study Visit will be reported to the safety database only, i.e. will not be included in the clinical database. A survival report form should be used for such reporting.

Post-study survival information will be collected as follows:

- Collection of survival data for the individual patient; at the 18 months post randomization time point
- A complete collection for all applicable patients; at the time of study end (*Section 7.5*)
- A complete collection for all applicable patients; at the last patient's 18 months post randomization time point and thereafter yearly up to 5 years

Updated information on median OS, will be reported to the authorities/IRBs/IECs as addendum(s) to the Clinical Study Report and also as part of the development safety update reports (DSURs).

11.4 SAE and SUSAR Reporting to CAs, IRBs/IECs, and Investigators

The Sponsor is responsible for informing all concerned CAs, IRB/IECs, and all clinical study investigators utilizing Intuvax of any individual case reports of SAEs that are determined to be reportable by the Sponsor (i.e. SUSARs). For a SUSAR that is fatal or life-threatening, this should be reported as soon as possible and not later than 7 days after the Sponsor was first advised, for any other SUSAR this should be within 15 days. In addition to SUSARs, the Sponsor is also responsible for reporting any unanticipated events that may place other patients or the study at risk.

The Investigator will ensure that all relevant information is provided to the Sponsor to allow the Sponsor to meet their obligations to report the SUSAR to the CAs and IRBs/IECs. Furthermore, it is the responsibility of the Investigator to comply with any applicable site-specific requirements related to the reporting of SAEs (other than SUSARs) involving his/her patients to the IRB/IEC that approved the trial. The Sponsor must obtain adequate documentation showing that the IRB/IEC was properly and promptly notified as required.

11.5 Dose Limiting Toxicity (DLT)

The following AEs are classified as DLTs:

- Any AE of CTCAE grade 3 or higher (except for fever CTCAE grade 4 as this is an expected sign of immunologic response after vaccination), and assessed as possibly or probably related to Intuvax within the interval between the first vaccination and the subsequent one (i.e. the DLT observation period)
- Any autoimmune reaction CTCAE grade 3 or higher probably or possibly related to Intuvax within the interval between the first vaccination and the subsequent one.

If a patient experiences an AE that is qualified as DLT after first vaccination the second dose of vaccine will not be administered to the patient, *Section 8.5*.

All DLTs, irrespectively of seriousness, must be reported to the CRO using the same procedures and in the same timelines as is applicable for SAEs.

A DLT should be reported as an AE assessed as possibly or probably related to Intuvax as applicable. If a DLT fulfils any criterion for an SAE it should be reported as such.

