This is the third Intuvax-study in man and the second study in mRCC patients. A phase I/II study in hepatocellular carcinoma patients is ongoing. Twelve (12) patients were included during 2012-2013 at one (1) study site in Sweden in the first phase I study in patients with mRCC referred for nephrectomy. The diagnosis was based on radiological presentation. No pretreatment biopsies from the kidney(s) were collected. Patients with prior autoimmune disease, with ongoing immunosuppressive therapy, or any other active cancer were

excluded. The patients' metastatic load varied. Five (5) patients were in the high-risk group and seven (7) in the intermediate group, according to the Heng prognostic model [4]. The Intuvax injections were performed with the patient hospitalized three (3) days to ensure safe care, collection of vital signs and blood samples. The vaccinations were performed twice, 14 days apart, in all patients. Nephrectomy was performed two (2) weeks after the second vaccination. Three (3) different dose levels of DCs; 5×10^6 , 10×10^6 , and 20×10^6 , were administered.

No serious adverse events (SAEs) related to the vaccination were noted. Transient fever reactions with duration less than one (1) day and rash was noted in 5 out of 12 patients. All patients survived the postoperative three (3) month follow-up visit. No significant deviations in blood chemistry attributable to the vaccination procedure were noted. Accidental bile duct injury was inflicted in one (1) patient resulting in transient hepatic failure. The renal function was decreased after nephrectomy in all patients as expected but no further decrease was observed except for one (1) patient who developed progressive renal function deterioration due to a previously undetected plasma cell disorder/myeloma. There were no signs of any autoimmune reactions as measured by standard tests while a humoral donor-specific alloimmunization was seen in three (3) patients.

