7.4 Study Period

Expected timelines in the study:

Start of inclusion: Q2 2015

Planned last patient last study visit or last patient's safety evaluation (up to 30 days after the last patient's last dose of an IMP), whichever occurs later: Q3 2019

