8.5 Removal of Patients from Therapy or Assessment

Patients are free to discontinue their participation in the study at any time. Withdrawal from the study will not affect or prejudice the patient's further care or treatment. Patients may be withdrawn from study treatment and assessments at any time, if deemed necessary by the Investigator.

Patients who discontinue treatment with Intuvax and/or sunitinib for safety reasons (including DLT, see *Section 11.5*) or due to concomitant medication (*Section 9.6*) will not necessarily be considered withdrawn from the study unless there are other reasons for withdrawal. They should return for all following visits and assessments until PD.

Examples of reasons for withdrawal of patients from this study are:

- Progressive disease on sunitinib treatment
- Screening failure
- The decision of a patient to withdraw from the study (i.e. if the patient withdraws informed consent)
- Administration of concomitant medication prohibited by this protocol, *Section 9.6*
- Pregnancy
- Patient is lost to follow-up
- RCC diagnosis is not confirmed by histological findings from the biopsy collected at nephrectomy or, if applicable, from confirmatory pre-study treatment diagnostic biopsy

The reason and date the patient is withdrawn from the study and subsequent planned replacement therapy will be documented in the electronic case report form (eCRF).

All patients that have received IMP must have safety evaluations for 30 days after the last dose of IMP, *Section 11.2*.

If a patient is withdrawn from further assessments, the Investigator should attempt to complete all discharge procedures, i.e. End-of Study Visit. All AEs should be followed up according to *Section 11.2*.

If a patient is withdrawn from the study, all data collected until the time of withdrawal will be used in the analyses.

Survival data (including post-study survival data if applicable) will be collected and analyzed for all patients withdrawn from the study, *Section 11.3*.

Patients randomized to Intuvax who withdraw from the study before administration of the first dose of Intuvax will be considered screening failures. Patients randomized to sunitinib alone who withdraw from the study before any assessments made at the first visit following Screening will be considered screening failures.

Only patients considered screening failures will be replaced.

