8.7 Study Stopping Criteria

Study stopping criteria are defined as:

- Any death within 30 days of Intuvax administration that is not clearly attributable to surgery or disease progression
- Any CTCAE grade 4 autoimmune disorder
- Any toxicity that is unexpected, significant or unacceptable risk to the patients enrolled in the study, or potential study patients, *Section 8.6*

The identification of a study stopping criterion in a patient will result in the permanent discontinuation of Intuvax in this patient and the enrolment will be temporarily held until an appropriate evaluation of the cause of the toxicity has been determined and a correction action plan is established if needed.

The medical monitor should be notified immediately and the patient should be followed for safety as clinically indicated until the toxicity resolves and in the opinion of the investigator, no further follow-up regarding the toxicity is needed (minimum of at least 30 days after last dose of IMP).

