9.4 Selection and Timing of Dose for Each Patient

The patients will be randomized to treatment when the results from all assessments made at Screening are available.

No time window between dosing of different patients applies in this study.

The time window between Intuvax doses for the individual patient is 14 ±3 days. If the individual patient experiences a DLT in connection with first vaccination, *Section 11.5* no second vaccination will be given to that patient.

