Minimal, local or noninvasive intervention indicated OR limiting age-appropriate instrumental Activities of Daily Living (ADL). (Instrumental ADL refer to preparing meals, shopping for groceries or clothes, using the telephone, managing money, etc.)

Grade 3 (Severe or medically significant but not immediately life-threatening)

Hospitalization or prolongation of hospitalization indicated OR disabling OR limiting self-care ADL. (Self-care ADL refer to bathing, dressing and undressing, feeding self, using the toilet, taking medications, and not bedridden.)

Grade 4 (Life-threatening consequences)

Urgent intervention indicated.

Grade 5 (Death related to AE)

If an AE changes in severity, the worst severity should be reported.

Causality

Causality will be assessed as:

Probable

A clinical event, including laboratory test abnormality, with a reasonable time sequence to administration of the IMP, unlikely to be attributed to concurrent disease or other drugs or chemicals, and which follows a clinically reasonable response on withdrawal (dechallenge). Rechallenge information is not required to fulfil this definition.

Possible

A clinical event, including laboratory test abnormality, with a reasonable time sequence to administration of the IMP, but which could also be explained by concurrent disease or other drugs or chemicals. Information on IMP withdrawal may be lacking or unclear.

Unlikely

A clinical event, including laboratory test abnormality, with a temporal relationship to IMP administration which makes a causal relationship improbable, and in which other drugs, chemicals or underlying disease provide plausible explanations.

Follow-up of Patients after Adverse Events

Any AE that is ongoing when the patient is withdrawn from the study should be followed up until the AE is resolved or the Investigator decides that the AE is stable and needs no further follow-up.

Abnormal Laboratory Values/Vital Signs

The reporting of abnormalities as both laboratory/vital signs findings and AEs should be avoided.

An asymptomatic abnormal laboratory/vital sign finding should only be reported as an AE if it is clinically significant, if it fulfils the criteria for an SAE or if it causes the patient to discontinue the study.

If an abnormal laboratory/vital sign value is associated with clinical signs and symptoms, the sign/symptom should be reported as an AE and the associated laboratory/vital sign result should be considered additional information.

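### The dose-limiting toxicity rule exempts grade 4 fever but not grade 3 fever, so the milder grade bars the second vaccine dose and the worse grade does not

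*Protocol*

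**What the plan says.** Protocol section 11.5 sets the DLT threshold at CTCAE grade 3, for any event judged possibly or probably related to Intuvax and occurring after the first vaccination and before the second. It makes one exception: "except for fever CTCAE grade 4 as this is an expected sign of immunologic response after vaccination". A second bullet adds autoimmune reactions of grade 3 or above and says nothing about fever.

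The consequence is stated twice. Section 11.5 says that after a DLT "the second dose of vaccine will not be administered to the patient". Section 9.4 refers to 11.5 and says "no second vaccination will be given to that patient".

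Section 11.2 gives the general meaning of the grades. Grade 3 is severe but not an immediate threat to life; grade 4 is life-threatening.

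Two other provisions could stop dosing. Section 8.5 says "Patients may be withdrawn from study treatment and assessments at any time, if deemed necessary by the Investigator". Section 8.7 lists among its stopping criteria "Any toxicity that is unexpected, significant or unacceptable risk to the patients enrolled in the study", and meeting a criterion ends Intuvax permanently for that patient and pauses enrolment.

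The SAP does not mention DLTs and plans no DLT table or listing.

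**The concern.** A rule for withholding a dose should be at least as strict for a worse event as for a milder event of the same kind. This one is not. If fever is excused because it signals the intended immune response, that reason covers grade 3 at least as well as grade 4, and no reading of it excuses grade 4 alone. The line looks like a drafting slip, but it is the operative text for deciding whether a patient receives a second intratumoral injection.

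Three things depend on it:

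- **Dosing.** Dose 2 after a grade 4 fever is not automatically withheld, while dose 2 after a grade 3 fever is.
- **DLT reporting.** DLTs go to the CRO by SAE procedures and timelines, so the line decides which between-dose fevers take that route.
- **Per protocol membership.** The per protocol set requires both Intuvax doses (Protocol 12.1.1, SAP section 5). A patient denied dose 2 for a grade 3 fever therefore leaves the set on which the primary analyses are repeated.

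**Working it through.** No power, sample-size or error-rate figure bears on this, and the plan gives no number to reproduce. The check is to apply 11.5 to each grade of fever, assuming the fever is related and falls between the doses.

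| Fever grade | Reaches the grade 3 threshold? | Exempt? | DLT? | Dose 2 under 11.5 and 9.4 |
|---|---|---|---|---|
| 1–2 | No | – | No | Allowed |
| 3 | Yes | No | Yes | Barred |
| 4 | Yes | Yes | No | Not barred by this rule |
| 5 (death) | Yes | No | Yes | Does not arise |

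The outcome goes from allowed to barred and back to not barred as severity rises.

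**Does anything correct it?** Section 3.2 sends the reader to 11.5 for DLT definitions. Section 9.4 only points to 11.5. The autoimmune bullet does not concern fever. No visible passage repairs the line. The risk table in 5.3 is redacted, so nothing can be inferred from it.

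**Is grade 4 fever supported as expected?** The phase I summary in 5.1 reports transient fever of under one day and rash in 5 of 12 patients, with no grades. It adds "No serious adverse events (SAEs) related to the vaccination were noted". That supports mild, short fever as expected. It does not single out grade 4.

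**How many patients?** With about 90 randomized 2:1, the vaccine arm is 90 × 2/3 = 60. The number with a grade 3 or 4 fever between doses is not in the documents.

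**Could the rule still affect dosing?** The inputs are:

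- planned last visit or last safety evaluation in Q3 2019, taken at its latest as 30 September 2019 (7.4);
- End-of-Study Visit at 78 ± 2 weeks after Screening (7.2.1.7);
- second vaccination by day 42, with Screening as day 1 (Table 2);
- protocol version 9.0 dated 12 February 2019 (SAP section 1).

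With the visit at 78 − 2 = 76 weeks:

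- latest Screening = 30 September 2019 − 532 days = 16 April 2018;
- latest second vaccination = 16 April 2018 + 41 days = 27 May 2018;
- interval to version 9.0 = 261 days.

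With the visit at 78 + 2 = 80 weeks:

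- latest Screening = 30 September 2019 − 560 days = 19 March 2018;
- latest second vaccination = 19 March 2018 + 41 days = 29 April 2018;
- interval to version 9.0 = 289 days.

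These dates are estimates. Section 7.2.1.6 turns a visit with progression into the End-of-Study Visit, so a patient screened later who progressed early could also finish within Q3 2019.

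**The case against.** The literal reading is hard to dispute. The case on the other side is about weight.

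- **Other safeguards apply.** The criterion in 8.7 is met by a toxicity that is unexpected, or significant, or an unacceptable risk. Calling fever expected weakens only the first of these, and a life-threatening related fever could well meet the others. The consequence under 8.7 is also stronger than a DLT. This stands, and it narrows the safety gap. It does not repair the rule: 8.5 and 8.7 do not name fever, and they do nothing for the reverse case, where grade 3 fever bars dose 2 automatically although the rationale in 11.5 would excuse it. The DLT rule also involves judgement on causality, but once causality is settled its consequence is automatic.
- **Fever has its own CTCAE description.** Section 11.2 notes that each event has specific grade wording, and that source is not among the documents. How dangerous a grade 4 fever is therefore cannot be shown here. The ordering can, because 11.2 says grade means severity, and the point needs only the ordering.
- **Fever handling could sit in the redacted part of 5.3.** This is possible. Certainty extends to the wording of 11.5, not to the absence of any other fever rule.
- **The practical effect may be nil.** This is fair. A life-threatening grade 4 fever is an SAE under 11.1.4 and reported as one under 11.3 whatever its DLT status, and no planned safety table depends on DLT status.

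**Conclusion.** The rule is wrong as written, and the matter is minor. Following 11.5 literally withholds dose 2 after the less severe fever and leaves it unbarred after the more severe one, for a reason that does not distinguish the two in that direction.

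The effect is confined to the second-dose decision in about 60 patients, to which between-dose fevers are classed and reported as DLTs, and, through dose 2, to per protocol membership. Endpoint definitions, full analysis set results and planned safety tables do not change. The number of patients affected is unknown and may be zero.

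The view that dosing had probably finished assumes that the supplied protocol is version 9.0 or its French counterpart 9.1 and that recruitment kept to plan. Earlier protocol versions are not available, so it cannot be said whether the same line applied when patients were dosed. If dosing is over, what remains is correct classification of past events and keeping the line out of any later protocol.

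**What to change.** Reword the exemption in 11.5 so that it never excuses a worse fever while penalising a milder one. The documents do not show which wording was intended, so the sponsor should choose and state one:

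1. **Exempt grade 3 fever only**, so that grade 4 fever is a DLT. This keeps the sponsor's rationale and closes the gap at the dangerous end, and is a reasonable default. It does relax the present bar after grade 3 fever.
2. **Delete the exemption**, so that both grades are DLTs. This is equally consistent and the most protective.
3. **Exempt grades 3 and 4**, only with a written justification from the medical monitor.

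Sections 9.4 and 3.2 only refer to 11.5 and need no change. Then re-check fevers reported between doses 1 and 2 against the corrected definition, noting any patient whose DLT status changes and whether dose 2 was given.

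The cost is one line of text and a review of between-dose fever reports in about 60 patients.

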11.6 Precautions/Overdose

Preparedness for anaphylaxis treatment in connection with vaccination is required. No antidote for Intuvax is available. In the event of overdose symptomatic management is indicated.

11.7 Pregnancy

Contraception is to be used from Screening until 90 days after last dose of Intuvax and/or until completed sunitinib treatment whichever occurs later.

Female patients will be instructed to notify the Investigator immediately if they become pregnant during the study. Male patients will be instructed to notify the Investigator immediately if their partner becomes pregnant. Pregnant patients will be withdrawn from further study treatment. The patients will also be instructed to report pregnancies discovered after the last visit, if they believe that conception occurred during their participation in the study.

A pregnancy as such is not an AE, unless there is a possibility that the IMP has interfered with the efficiency of any contraceptive measures. However, the Investigator should report pregnancies according to the procedures and timelines described for reporting of SAEs (*Section 11.3*). The pregnancy report form should be used instead of the SAE form.

The pregnant patient or partner will be followed until the end of the pregnancy. Any complication during the pregnancy should preferably be reported as an AE. The outcome of the pregnancy must be reported on the pregnancy report form. Any spontaneous abortion, stillbirth, birth defect/congenital anomaly, death, or other serious infant condition must be reported and followed up as an SAE.

12 STATISTICAL METHODS AND DETERMINATION OF SAMPLE SIZE

12.1 Statistical and Analytical Plans

A separate SAP, which will provide the technical details of the statistical analysis outlined below, will be prepared and approved before study data analysis, including any interim analysis.

12.1.1 Data Sets to be Analyzed

The analysis population sets, which will be defined separately by stratum, are defined as follows:

Full analysis set (FAS): All patients randomized being evaluable for any high or intermediate stratum related efficacy endpoint.

Per protocol set (PPS): All patients randomized to Intuvax who had both doses of Intuvax administered or subject randomized to sunitinib alone, both having the nephrectomy and who continued the trial without any major protocol violations that could interfere with the objectives of this study.

Analyses of primary endpoints related to each stratum will be repeated using the PPS.

Subgroups will furthermore be defined separately by stratum, as patients exposed to at least one dose of sunitinib and having following evaluable PFS.

Safety set: All randomized patients who have at least one (1) assessment made at Screening.

Safety summaries will be performed on the safety set.

